3.1.1 Dose Optimization Phase

The Dose Optimization Phase will be conducted at up to approximately 15 centers in the US.

In the Dose Optimization Phase, patients will be randomly assigned at a 1:1 ratio to 1 of 2 study cohorts, as follows:

- Cohort 1: Duvelisib orally (PO) twice daily (BID) at a starting dose of 25 mg, with potential escalation on a per-patient basis to 50 mg BID and then 75 mg BID, based on the patient's response to and tolerance of therapy, in 28-day cycles.
- Cohort 2: Duvelisib 75 mg PO BID, administered in 28-day cycles.

Approximately 10 patients each will be enrolled in Cohorts 1 and 2. Patients in the Dose Optimization Phase who discontinue before receiving at least 1 cycle of study drug may be replaced. Enrollment into the Dose Optimization Phase may continue until the initiation of the Expansion Phase.

For both cohorts, dose modification criteria for duvelisib will be applied if the starting dose or a subsequent dose of Duvelisib is deemed intolerable (see Section 8.4.2 of the Clinical Study Protocol (CSP)). Dose Optimization Phase patients will complete treatment as defined for their cohort.

Cohort 1

All patients will receive duvelisib at a starting dose of 25 mg PO BID (Level 1), with potential sequential escalation to 50 mg PO BID (Level 2), and then to 75 mg PO BID (Level 3). Intrapatient dosing decisions will occur as follows:

- After completion of Cycle 1 and every 2 cycles thereafter:
 - Patients with CR or PR will have their duvelisib dose maintained at the current dose level.
 - Patients with stable disease (SD) who are, in the Investigator's opinion, tolerating and otherwise suitable to continue receiving therapy, will have the duvelisib dose increased to the next level until the next response assessment or development of PD or intolerance, as determined by the Investigator.
- Patients with PD who are not, in the Investigator's opinion, tolerating therapy or otherwise not suitable to continue receiving therapy will discontinue duvelisib.

In no case will the duvelisib dose be increased to a level > 75 mg BID (total daily dose 150 mg).

All patients in Cohort 1 will receive duvelisib until development of PD or unacceptable toxicity, as determined by the Investigator.

Cohort 2

All patients in Cohort 2 will receive duvelisib 75 mg PO BID in 28-day cycles until development of PD or unacceptable toxicity, as determined by the Investigator.

3.1.2 Expansion Phase

The Expansion Phase will be conducted at approximately 40-50 centers globally.

At the conclusion of the Dose Optimization Phase, efficacy, PK, and safety data as well as any other available data will be taken into consideration to recommend the optimal dose for the Expansion Phase. In addition to recommending an optimal dose, the Expansion Phase may also involve modifications of the study patient population, other aspects of entry criteria, and the inclusion of patients from geographic regions outside the United States (US); any such changes will be documented in an amendment to the protocol. Patients will have disease assessment after Cycle 2 and every 2 cycles thereafter until the follow-up stage is reached and assessment will occur according to Table 4 of the CSP.

With protocol amendment 7.0, 20-30 additional patients will be enrolled in the Expansion Phase for a total of up to 130 patients.

Expansion Phase Dose Selection:

As of January 2, 2019, 20 patients met the criteria for the Dose Optimization efficacy population and available data as of February 11, 2019, was reviewed. A dosage of 75 mg BID for the first 2 cycles, followed by a mandatory reduction to 25 mg BID thereafter for those patients with CR, PR or SD, will be used for the Expansion Phase. The dose may be re-escalated to 75 mg BID based on response assessment and safety (see CSP Sections 1.3 and 8.1.2).

3.2 Randomization

In the Dose Optimization Phase only, patients will be randomly assigned on C1D1 to either Cohort 1 or 2 on a 1:1 basis via a computer-generated randomization scheme. No stratification methodology will be employed in this study.

3.3 Sample Size Considerations

Approximately 20 patients will be enrolled in the Dose Optimization Phase, with approximately 10 evaluable patients per cohort. However, enrollment may discontinue in either cohort if no CR/PR, as assessed by the Investigator, is noted in the first 5 evaluable patients per cohort. This stopping rule is based on the first stage decision rule of a Simon 2-stage design, with assumptions of a hypothesized ORR of 50% and a null rate of 15% with a one-sided alpha of 0.05 and a power of 85%.

Patients in the Dose Optimization Phase who discontinue before receiving at least 1 cycle of study drug may be replaced.

In the Expansion Phase, the target enrollment is approximately 100 patients with a centrally confirmed diagnosis of PTCL. It is anticipated up to 5% of patients may have a diagnosis that is not confirmed upon central pathology review. One-hundred patients will provide 99.2% power to distinguish between a null ORR of 20% and an alternative ORR of 40% with a two-sided alpha of 0.05. Further, with 100 patients treated at the optimal duvelisib dose, the obtained ORR will have 95% confidence bounds of no greater than \pm 10% when the normal approximation method is employed (assumes 50% ORR). If the observed ORR is greater or less than 50%, the confidence bounds will be less than \pm 10%. These bounds around the obtained ORR are thought to adequately characterize the effect of the optimal dose of duvelisib in this PTCL population.

With protocol amendment 7.0, 20-30 additional patients will be enrolled in the expansion phase. Assuming a total of 120 or 130 patients the power to distinguish between a null hypothesis of ORR of 20% and an alternative ORR of 40% will be 99.4% or 99.6%, respectively.

The primary analysis for the Expansion Phase will be performed once approximately 100 patients with a centrally confirmed diagnosis of PTCL have been enrolled and evaluated for the primary endpoint. In the event that enrollment in the expansion phase exceeds 110% of the planned sample size, a sensitivity analysis will be performed on the first 100 patients enrolled in the Expansion Phase.

The final analysis for the Expansion phase will be performed once all patients with a centrally confirmed diagnosis of PTCL have been enrolled and evaluated for the primary endpoint. The total number of patients (up to 130) will be determined by the Sponsor. An important driver of the final sample size may be the number of additional patients needed to add an additional 8-10 patients having PTCL subtype of either ALCL or NK cell.

3.4 Blinding

No blinding of treatment assignment will be used in this study.

3.5 Interim Analysis and Data Review

As noted in Section 3.3, during the dose optimization phase, the ORR for each dose optimization cohort will be reviewed when 5 patients are determined to be evaluable. If no response of CR or PR has been observed in the cohort then enrolment in that cohort will be discontinued. Evaluation of response in this analysis will be based on Investigator assessments.

In addition, at the conclusion of the Dose Optimization Phase, all available data will be reviewed and an optimal dose for the Expansion Phase will be selected. In addition to recommending an optimal dose, the Expansion Phase may also involve modifications of the study patient population, other aspects of entry criteria, and the inclusion of patients from geographic regions outside the US; any such changes will be documented in an amendment to the protocol. The Sponsor study team, in collaboration with the Investigators, will make the determination of duvelisib dose for the Expansion Phase of the study based on the totality of available safety and activity data. This evaluation does not constitute an interim analysis.

During the expansion phase, two assessments of ORR will be conducted. The first will be a preliminary assessment of ORR after approximately 15 subjects have had an initial assessment of response by the investigator. During this assessment, the data from the expansion phase will be reviewed in the context of data from the dose optimization phase.

The second assessment will occur after 40 patients have been followed for a minimum of 4 months from the last patient's first dose and assessed for response by the IRC. At that time, enrollment in the Expansion Phase may be held if ORR is less than 20%. The efficacy data (including durability of response) will be reviewed in combination with safety and PK and upon review, the study may be fully stopped for futility.

- Additional interim analyses will be used for planning purposes, FDA submission and discussion and possible publication of early efficacy and safety results. The final analysis of the study will be completed and submitted to health authorities and published as appropriate. The approximate timing of these interim analyses are when: At least 75 of expansion phase patients have been followed for a minimum of 6 months from the last patient's first dose and assessed for response by the IRC.
- All patients enrolled prior to protocol v7.0 (101 patients) who have been followed for a minimum of 6 months from the last patient's first -scheduled response assessment (*i.e.*, 8 months from their first dose) and who have response assessed by the IRC.

3.6 Analysis Sets

3.6.1 Dose Optimization Efficacy Set

Dose Optimization Efficacy Set will consist of all patients who 1) receive at least one dose of study drug and 2) complete at least one cycle of treatment and 3) have at least one scan to assess disease response after completion of one cycle of treatment.

Efficacy analyses for the dose optimization phase will be performed using the Dose Optimization Efficacy Set for all primary and secondary efficacy analyses using the response determined by the Investigator. The IRC's determination of disease response will be used in supportive efficacy analyses.

3.6.2 Modified Intent-to-treat (mITT) Analysis Set

The mITT Population will consist of patients who receive at least one dose of study drug.

Efficacy analyses for the dose expansion phase will be performed using the mITT Analysis Set for all primary and secondary efficacy analyses using the response determined by IRC.

3.6.3 Safety Analysis Set

The Safety Population consists of all patients receiving at least 1 dose of duvelisib.

Safety analyses will be performed using the Safety Analysis Set.

4 General Statistical Methods and Data Handling

4.1 General Methods

Summary statistics will be presented by treatment group, unless stated otherwise.

Unless otherwise specified, descriptive statistics for continuous data will include the number of subjects with data to be summarized (n), mean, standard deviation, 25% quartile, median, 75% quartile, and minimum and maximum. The same number of decimal places as in the raw data will be presented when reporting the minimum and maximum, one more decimal place than the raw data will be presented when reporting mean and median, and 2 more decimal places than the raw data will be presented when reporting standard deviation.

Descriptive statistics for categorical/qualitative data will include frequency counts and percentages. The total number of subjects in the treatment group will be used as the denominator for percent calculations, unless stated otherwise. All percentages will be presented with one decimal, unless otherwise specified. Percentages equal to 100 will be presented as 100, and percentages will not be presented for zero frequencies.

Descriptive statistics associated with time-to-event analyses will include the number of events, the number of subjects censored, 25% quartile, median, 75% quartile, and 95% confidence interval for median. These statistics will be presented for all time-to-event analyses, unless stated otherwise.

Listings will be provided for selected endpoints.

4.2 Treatment-emergent Adverse Event (TEAE) Definition

An Adverse Event (AE) is defined as any untoward medical occurrence in a patient administered a medicinal product that does not necessarily have a causal relationship with this treatment. An AE can, therefore, be any unfavorable and unintended sign (including an abnormal laboratory finding), symptom, or disease temporally associated with the use of a medicinal (investigational) product, whether or not related to the study (investigational) product. This includes an exacerbation of pre-existing conditions or events, concurrent illnesses, drug interaction, or the significant worsening of the indication under investigation. Anticipated fluctuations of pre-existing conditions, including the disease under study that does not represent a clinically significant exacerbation or worsening, need not be considered AEs.

Symptoms of the disease under study / lack of efficacy / disease progression should not be classified as an AE as long as they are within the normal day-to-day fluctuation or expected progression of the disease.

The onset date of an AE will be compared to the first dose date and the last dose date plus 30 days (inclusive) to determine whether the AE is treatment-emergent or not. Adverse events occurring on the first dose date will be considered treatment emergent unless otherwise indicated on the eCRF.

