# 4. STUDY DESIGN

# 4.1. Overview of Study Design

This is a multi-center, parallel cohort, open-label, Phase 2 study of duvelisib, an oral dual inhibitor of PI3K- $\delta$ , $\gamma$ , in patients with relapsed/refractory PTCL. The study has 2 phases, a Dose Optimization Phase and an Expansion Phase.

Regardless of study phase, all patients will undergo screening assessments up to 30 days before the first study drug dose (Cycle 1, Day 1 [C1D1]). Patients meeting all of the entrance criteria, based on Screening assessments, will be enrolled in the study and receive the first study drug dose on C1D1. Thereafter, patients will attend study center visits as per the applicable Phase Schedule of Events (Dose Optimization: Table 1, Expansion Phase: Table 2). At screening, disease will be measured using F-fluorodeoxyglucose-positron emission tomography (FDG-PET)-computed tomography (CT) scanning (PET-CT) (CT images along with PET should be diagnostic with contrast unless contraindicated). Where PET-CT is not feasible, CT with contrast or magnetic resonance imaging (MRI) may be used after discussion with the Medical Monitor. Subsequently, for FDG-avid PTCL, PET-CT will be used to assess disease status and for FDG-non-avid PTCL, CT with contrast or MRI will be appropriate substitutes. The modality chosen to evaluate response in each individual patient should be the same throughout the duration of the study. For the purposes of patient management during the conduct of the study, the Investigator's assessment of disease response will be used. Images also will be centrally stored, and disease response will be determined by an IRC for futility and at the end of the study.

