# **10.3.** Reporting of Adverse Events and Serious Adverse Events

The AE reporting period begins from the time that the patient signs the ICF through and including 30 calendar days after the last study drug dose. All treatment-related AEs/SAEs should be followed until resolution or stabilization. Any SAE occurring after the reporting period must be promptly reported if a causal relationship to the investigational drug is suspected. If the patient begins a new anticancer therapy, the safety reporting period ends at the time the new treatment is started, however, death must always be reported if it occurs during the AE reporting period irrespective of intervening treatment.

Elective or previously scheduled hospitalizations for pre-existing conditions that have not worsened after initiation of treatment should not be classified as SAEs. For example, an admission for a previously scheduled ventral hernia repair would not be classified as an SAE.

All AEs should be recorded individually unless, in the opinion of the Investigator or designated physician, the AEs constitute components of a recognized condition, disease, or syndrome. In the latter case, the condition, disease, or syndrome should be reported rather than each individual sign or symptom. If a constellation of signs and/or symptoms cannot be medically characterized as a single diagnosis or syndrome at the time of reporting, each individual event should be recorded as an AE or SAE as appropriate on the relevant form(s) (SAE Report Form and/or AE eCRF). If a diagnosis is subsequently established, it should be reported as follow-up information is available. If a diagnosis is determined subsequent to the reporting of the constellation of symptoms, the signs/symptoms should be updated to reflect the diagnosis.

Each AE is to be evaluated for duration, severity, seriousness, and causal relationship to the investigational drug. The action taken with study drug and the outcome must also be recorded.

All SAEs, regardless of relationship to the study treatment, must be reported immediately to the Sponsor and Contract Research Organization (CRO) pharmacovigilance group, with the timeframe not to exceed 24 hours of the Investigator becoming aware of the event. Initial SAE

notification should be made by e-mailing or faxing the SAE report form to the e-mail or fax number provided on the SAE report form.

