4.3 Handling of Missing Data

4.3.1 Handling of Missing Dates/Months/Years for Determination of TEAEs

Adverse events with incomplete onset dates will be handled as follows for the purpose of determining treatment emergence according to the definition above.

- If the start/end date of an AE is partially missing, the date will be compared as accurately as possible with the first dose of study drug and the date of last dose of study drug plus 30 days. The AE will be assumed to be treatment-emergent if it cannot be definitively shown that the AE did not start or worsen during the treatment-emergent period.
- If the start date is completely missing, an AE will be considered treatment-emergent unless the stop date is before first dose of study drug.

The original partial or missing date will be displayed in listings of AEs.

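### SAP 4.2 decides treatment emergence by onset date only, but SAP 4.3.1 counts worsening for partial dates, so an AE that starts before dosing and worsens on duvelisib is classed by how complete its date is

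*SAP*

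**What the plan says.** The protocol lists TEAEs as a secondary endpoint in both phases but does not define the term. The only definition is in SAP 4.2, and it works on the onset date: "The onset date of an AE will be compared to the first dose date and the last dose date plus 30 days (inclusive". One qualifier follows, for Day 1 events: "Adverse events occurring on the first dose date will be considered treatment emergent unless otherwise indicated on the eCRF". Neither sentence mentions an AE already present at first dose that later increases in grade.

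SAP 4.3.1 deals with incomplete dates and ties itself to the preceding section: "Adverse events with incomplete onset dates will be handled as follows for the purpose of determining treatment emergence according to the definition above". For a partially missing date it presumes treatment emergence "if it cannot be definitively shown that the AE did not start or worsen during the treatment-emergent period". For a wholly missing start date the rule is: "If the start date is completely missing, an AE will be considered treatment-emergent unless the stop date is before first dose of study drug".

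AE records can pre-date treatment. Protocol 10.3 states: "The AE reporting period begins from the time that the patient signs the ICF". Protocol 4.1 states that "all patients will undergo screening assessments up to 30 days before the first study drug dose".

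**The concern.** SAP 4.3.1 claims to apply the 4.2 definition but uses a wider one. The same clinical course can therefore fall on either side of the TEAE line according to how well the site recorded a date. The use of worsening in 4.3.1 suggests that the authors meant it to count, and that 4.2 omits it by oversight.

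The flag drives most of the AE reporting. In SAP 5.3.1 the all-grade, Grade 3 or higher, treatment-related, dose-hold, dose-reduction, discontinuation and fatal-event tables are TEAE tables. So are most of the grouped-risk summaries in SAP 5.3.1.1. For complete dates the error runs one way: the rule can remove an on-drug worsening from these tables but cannot add one.

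**Working it through.** The plan gives no figure to reproduce, so the check is to apply both rules literally to one test event.

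**Inputs**
- Window: first dose to last dose plus 30 days (SAP 4.2).
- AE collection starts at consent (Protocol 10.3); Screening lasts up to 30 days (Protocol 4.1).
- Test event, assumed for illustration: a rash that begins on Day -5 at Grade 1, reaches Grade 3 during treatment, has not stopped before first dose, and is kept as one eCRF record with its original onset date.

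**Results**

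| Case | Rule | Classification |
|---|---|---|
| (a) Onset date complete | 4.2: Day -5 is before first dose | Not a TEAE |
| (b) Onset date partial, worsening in the window not excluded | 4.3.1, partial date | Presumed TEAE |
| (c) Start date wholly missing | 4.3.1, missing date; not stopped before first dose | TEAE |
| (d) Worsening entered as a separate AE with on-treatment onset | 4.2 | New record is a TEAE; the original is not |

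**Reading the table**
1. Cases (a) and (b) are the same clinical event; only the completeness of the date differs.
2. Case (b) can turn wholly on worsening. Suppose the day is missing but the recorded month is earlier than the month of first dose. Onset in the window is then ruled out, yet 4.3.1 still presumes a TEAE because worsening has not been ruled out. Under 4.2 as written, such an event could not qualify.
3. If 4.2 used the same start-or-worsen test, case (a) would be a TEAE and the conflict would disappear.
4. Case (d) shows that nothing is lost if sites enter each worsening as a new AE. SAP 4.2 and Protocol 10.1 count an exacerbation of a pre-existing condition or event as an AE, which permits this. No section requires a new record when the grade of an AE already on file changes. Protocol 10.3 asks for each AE's duration and severity and is silent on changes in grade.

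**The case against.** The strongest reply is that the SAP already captures these events. Because an exacerbation is itself an AE, its onset is the day it occurs; if that is on drug, 4.2 flags it. Protocol 6.6 works in a similar way: significant examination abnormalities found in Screening go to medical history, and a clinically significant finding that worsens after consent is reported as an AE. This stands as a limit. The loss occurs only where the worsening stays on the original record, and the eCRF convention is not given. It does not remove the conflict between 4.2 and 4.3.1.

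A reader might go further and infer that pre-dose AEs will be common because entry allows residual Grade 1 toxicity, AST/ALT up to 3 x ULN, platelets from 25 x 10^9/L and transfused haemoglobin. The documents do not support this. Those are mostly conditions already present at entry, not AEs that begin after consent. Protocol 10.6 makes a laboratory value an AE only if it is clinically significant, above Grade 2, and accompanied by intervention, a change in study drug or symptoms. AST/ALT within the entry limit lies below the Grade 2 band in Protocol Table 8, so a later qualifying rise would be a new AE with on-treatment onset. The narrower case that survives is a cytopenia that already meets 10.6 between consent and first dose. An example is Grade 3 thrombocytopenia transfused in Screening that reaches Grade 4 on drug. Non-laboratory AEs such as rash or diarrhea that begin in that interval also remain.

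A reader might also infer that every AE table is affected. That is too broad. SAP 5.3.1 includes Grade 3 or higher, Grade 3, Grade 4 and all-SAE tables that are not labelled treatment-emergent, and listings of all AEs and all SAEs in which TEAEs are only flagged. SAP 5.3.8 defines on-treatment deaths by the timing of death. SAP 5.3.2 tabulates on-treatment laboratory worsening in grade from baseline whatever the AE flag says; clinical AEs have no equivalent table.

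**Conclusion.** The inconsistency is real and should be corrected. SAP 4.2 and 4.3.1 use different definitions. A pre-dose AE that worsens on duvelisib under one record is left out of the TEAE tables when its date is complete and presumed in when its date is partial.

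The undercount rests on three conditions: the AE begins after consent and before first dose; it worsens in grade in the window; and the eCRF keeps one record with the original onset date. The documents give no frequency for the first two and no convention for the third, so no percentage can be attached. The mitigations make a small effect likely, and the effect is nil if every worsening is entered as a new AE. The primary endpoint and its analysis are unaffected; the safety tables are descriptive.

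**What to change.** 1. In SAP 4.2, define a TEAE as an AE that starts, or worsens in grade, on or after first dose and up to 30 days after last dose. Keep the Day 1 eCRF qualifier.
2. In SAP 4.3.1, apply that same definition to incomplete dates, so that both sections use one test.
3. State how a grade change is identified: by a new AE record, or by the date of grade change if the eCRF holds it. If it holds neither, say so as a limitation.
4. State which date enters the time-to-onset summaries in SAP 5.3.1.1, where time to initial onset is AE start date less first dose date plus 1. For the test event the original onset would give -5 + 1 = -4 days, so the worsened episode needs its own date there.

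The cost is a short SAP revision and a small programming change, provided that grade changes can be identified in the data. TEAE rates may rise slightly.
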